1.2.2. Neso-gastro (ng) tube positioning

Although generally safe and effective, NG tubes are usually inserted blindly at the bedside and there is a wide spectrum of known complications associated with feeding tube placement. The most common serious complication is misplacement of the feeding tube into the bronchial tree with resulting pneumonitis, pneumonia, and/or pneumothorax if not recognized. This is reported to occur in 2.4%–3.2% of nasogastric insertions. The rate of migration of jejunal placement back to the duodenum or stomach is 27%–42%⁷.

It is estimated that approximately 1.2 million feeding tubes are placed each year in the United States alone. If these tubes were placed blindly this would translate to 3,600 to 8,400 pulmonary injuries, and 1,200 to 3,600 deaths in the United States each year.

Positioning complications also occur throughout the duration of the use of the tube. Movement of the distal tip of the feeding tube occurs even when the NG tube is taped in place. This is most likely to occur with soft, small-bore NG tubes. Malpositioning of the indwelling tube may result in injury or aspiration.

1.2.3. Aspiration pneumonia

The central cause of aspiration pneumonia in tube-fed patients is due to aspiration of gastric contents. There are various tube-fed nursing practices that may help reduce the rate of aspiration, but their efficacy is limited and they are hard to implement. Currently there are no device-based solutions for preventing or monitoring gastric content aspiration. Many researchers agree that aspiration of gastric contents in tube-fed critically ill patients is of greatest concern.

⁵ McClave et al. Guidelines for the Provision and Assessment of Nutrition Support Therapy in the Adult Critically Ill Patient: Society of Critical Care Medicine (SCCM) and American Society for Parenteral and Enteral Nutrition (A.S.P.E.N.). *Jou Par Ent Nutr.* Vol 40/2 Feb 2016 156-211. DOI:10.1177/0148607115621863.

⁶ Bendavid I, et al., NutritionDay ICU: A 7-year worldwide prevalence study of nutrition practice in intensive care, *Clinical Nutrition* (2016), <http://dx.doi.org/10.1016/j.clnu.2016.07.012>.

⁷ Feeding Tube Placement: Errors and Complications. *Stayner JL et al. Nutr Clin Pract* (2012)

Subject: smART Plus Comparative Study Protocol - Beilinson

A study on 329 ventilated and tube fed patients from 2010 shows that 88% have at least one instance of gastric content aspiration during the three days monitored⁸.

The cost saved per patient per feeding tube: 8K\$ (x-ray, GRV, food loss, extended hospital stay).

1.2.4.Acute kidney injury (AKI)

Acute Kidney Injury (AKI) is an umbrella term for any abrupt decrease in Kidney function, encompassing several kidney diseases as well as combinations of such diseases.

Hospital AKI is a significant risk factor for in hospital mortality. It is estimated that AKI affects between 7-18% of hospital inpatients. Among critical ill patient the prevalence goes up to 30-70%. The same study showed that as many as 23.5% cases of hospital AKI went unrecognized.

1.3. Device Description

The smART+ is a comprehensive modular patient care system intended for ICU patients. At the heart of the system is the console which stores, compiles and displays data from the different system modules.

Directly connected to the console is the hub, this is a smaller unit that is positioned adjacent to the patient's bed and serves as a mechanical and communications port for the various modules.

The system's modular arrangement allows the flexibility to add modules over time, at this stage the system comprises the following modules:

- a) The feeding pump is an integral part of the systems console. The feeding pump is controlled by the console and programed by the user using the console's touch screen.
- b) To correspond with the feeding pump, a single use feeding set equipped with an appropriate administration cassette, is loaded into the console.
- c) The feeding tube is equipped with sensors that guide the user toward proper placement of the feeding tube without the need of a conformational x-ray. The sensors also detect reflux events and conveys that information to the console. A balloon on the feeding tube's exterior may be inflated at times of reflux in order to hinder the advancement of gastric content in the esophagus and prevent it from reaching the patient's lungs.
- d) To relieve pressure and remove access gastric content, a disposable Gastric Residual Volume (GRV) set is connected to the proximal end of the feeding tube. The GRV tube passes through a pinch on the system's hub and is only opened when necessary.
- e) The Resting Energy Expenditure (REE) feature is comprised of a disposable flow rate meter and a reusable CO2 detector piece that are added between the patient's endotracheal tube and ventilation tubes. The REE has the capacity to continually measure the patient's energy

[figure not shown]
⁸ Metheny. Effectiveness of an Aspiration Risk-Reduction Protocol. *Norma A. Nurs Res* (2010)

Subject: smART Plus Comparative Study Protocol - Beilinson

expenditure and deduce the patient's nutritional requirements, according to the following equation:

$$REE = \left[3.941 \left(\frac{VCO_2}{RQ} \right) + 1.11(VCO_2) \right] 1.44$$

f) The urineFlow disposable set connects to a urinary catheter, relaying urine through a tube and down to a viewing chamber into a collection bag. The viewing chamber is securely inserted into the urineFlow unit which is positioned horizontally off the patient's bed or on an adjacent IV pole. Drops falling through the chamber are captured by a camera mounted in the unit. The images are processed and the drop volumes are calculated and subsequently the patient's urine output rate is monitored. The urineFlow unit also includes a stabilizing mechanism to ensure that the unit is perpendicular to the ground at all times.

1.4. Intended Use

Europe: The smART+ System is a feeding optimization system that contains an anti-reflux mechanism, which uses the smART+ Feeding Tube with sensors to prevent gastric content from regurgitating to the esophagus and aspirating into the lungs. The system is intended to be used in healthcare setting.

USA: The smART+ System is a feeding optimization system that contains an anti-reflux mechanism, which uses the smART+ Feeding Tube with sensors and balloon to reduce gastric content from regurgitating to the esophagus. The system is intended to be used in healthcare setting.

1.5. Intended Users and Training Requirements

The smART+ System is indicated for the same patient population as other commercially available feeding tubes, namely, patients in need of enteral feeding and administration of medications. The

Subject: smART Plus Comparative Study Protocol - Beilinson

smART+ feeding tube will be introduced to patients by the medical staff qualified to introduce commercially available feeding tubes. During site initiation, all site staff that have been identified as device operators will receive training by the sponsor in order to ensure correct use of the device throughout the study.

1.6. Manufacturer and Manufacturing Information

The smART+ System was designed and is manufactured by Art Medical. Details on the manufacturing of the system are provided in the Investigator's Brochure.

1.7. Device Procedure

The use of the smART+ System is substantially similar to the use of commercially available feeding tubes. The smART+ System includes the added feature of facilitating correct tube placement and alerting when tube is displaced during ongoing use. The system will automatically stop feeding if displacement is detected. If a reflux episode is detected by the system, a balloon located on the tube will automatically inflate to prevent gastric content from regurgitating to the esophagus. The balloon inflation parameters are as follows:

- Maximum balloon pressure: 30 mmHg
- Maximum inflation duration: 5 minutes
- Minimum duration between balloon inflations: as long as the previous inflation period

In addition to tube placement, the system allows to obtain REE measurements and calculates the optimized nutritional values required by the patient. Furthermore, the system optimizes feeding by compensating for any lost feeding time or discarded nutritional content that was discarded via the GRV.

1.8. Risk/Benefit Assessment

1.8.1. Known potential risks

The smART+™ System is designed according to international standards for medical devices.

Compliance with these standards ensures that the device can be used safely in humans.

Biocompatible materials are used for the smART+ disposables that come in any direct or indirect tissue contact.

In addition, the results from previous studies supports the company's claim that the insertion, balloon inflation and feeding with the smART™ feeding tube are safe and tolerable. The results also show that the automatic GRV operates properly and efficiently, and the feeding tube device aids in the correct placement of the feeding tube into the patient.

[figure not shown]
ART Medical follows and complies with the risk management standard ISO 14971:2012 and ISO 14971:2007. Extensive design verification & validation bench and animal tests were performed to mitigate all risks detected, in accordance with essential requirements listed in the Medical Device Directive (MDD 93/42/EEC). The complete risk management document is available from the company upon request.

1.8.2. Known potential benefits

Subject: smART Plus Comparative Study Protocol - Beilinson

As explained above, the various components of the smART+ System must operate as a cohesive system in order to allow feeding optimization as demonstrated in the flowchart below. With validation of the smART+ features during the study, the clinical benefit of the device will be the lowering of risks associated with tube displacement and malpositioning as well as lowering the risks associated with reflux and aspiration.

In addition, the smART+ System is able to continuously measure the patients REE and minimize the risk of overfeeding. Therefore, by reducing overfeeding it not only achieves feeding optimization, but it also reduces the likelihood of reflux episodes due to overfeeding.

2. Objectives and Endpoints

2.1. Primary Endpoint:

 ART MEDICAL PATIENT SAFETY TECHNOLOGY	Number: CRO-C-2822	Date issued: 01-Mar-2021
	Rev.06	Page 15 of 35

Subject: smART Plus Comparative Study Protocol - Beilinson

Optimization of the delivery of nutrition by the smART+ System as compared to standard of care, by automatically calculating and administering enteral feeding better than standard of care (REE or Calorimeter).

Optimization is defined as the ability of the system to provide adequate nutrition (not overfeed or underfeed) when compared to treatment via standard of care.

Evaluation will be conducted based on an analysis and comparison of the following parameters (obtained through the hospital's electronic records for control group and smART+ records for the treated group):

- Patient caloric target set
- Volume of patient nutritional intake value versus actual patient need – this is calculated by assessing the actual nutrition delivered, discarded nutrition in the GRV bags as well as the unused quantity in discarded feed bottles (if applicable).

As part of optimization evaluation, feeding efficiency calculation ((Net nutrition delivered [ml])/ (VTBD [ml])) should be calculated for the days when the patient received enteral feeding that given under medical order, removed from the patient, or stopped feeding that was not renewed until the end of the study. Feeding efficiency should not be calculated for the days that patient has been discontinued from enteral feeding by a medical order.

2.2. Secondary Endpoints:

- Safety

Safe use of the entire system will be assessed based on the occurrence of device related AE or SAE.

- Decrease in ICU length of stay.

Measured from admission to ICU until the decision to discharge is ordered.

- Reduction of VAE According to the definition from the latest CDC.
- Decrease in ventilation days.

Evaluated by the number of hours of etCO2 from the hospital electronic records

- Decrease in workload related to nurse GRV time.

Patient GRV information obtained through the hospital's electronic records and the usability questionnaires, will be analyzed to determine (a) the estimated nursing time that was expended for GRV activities, and (b) the amounts of GRV removed from the patient.

- Convenience of use of the system and the user interface (by subjective staff questionnaire)

Evaluated via questionnaires filled by physician users and nurse users participating in the study.

- Assessment of urine flow monitoring related to patient condition and usability

Patient lab results obtained through the hospital's electronic records and the usability questionnaires, will be analyzed against smART+ system urine alerts, to determine if the alerts will be useful in diagnosis and usability satisfaction.

 ART MEDICAL PATIENT SAFETY TECHNOLOGY	Number: CRO-C-2822	Date issued: 01-Mar-2021
	Rev.06	Page 16 of 35
Subject: smART Plus Comparative Study Protocol - Beilinson		

3. Study Design

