1.2. The Problems/Study Rationale

1.2.1. Malnutrition in the ICU

Many critically ill patients develop malnutrition during hospitalization. Malnutrition is a complication which adversely affects clinical outcomes, including length of hospital stay, morbidity, and mortality. The characteristics of ICU patients have changed during the last decade; they now tend to be older and their medical disorders more complex with frequent comorbidities. These factors may contribute to malnutrition in the ICU. Additionally, the combination of stress and undernutrition is associated with negative energy balances and the loss of lean body mass².

Mechanically ventilated patients are unable to take food orally and therefore are dependent on enteral nutrition for provision of both energy and protein requirements. Many critically ill patients often have pre-existing conditions, including malnutrition. All of this predisposes patients to nutrition deficits, muscle wasting, delayed wound healing, slower recovery, and increased risk of morbidity and mortality. There is a consensus that supplemental nutrition support is needed and improves outcomes for patients³.

Providing adequate energy via nutrition support to the mechanically ventilated patient is critical. In the mechanically ventilated patient, overfeeding, even for short periods of time, can lead to hyperglycemia and increases time on the ventilator. Conversely, an increasing caloric deficit (persistent underfeeding) also increases time on the ventilator. Providing early nutritional intervention may shorten hospital stays by 2 days, lower readmission rates by 27% and save \$3,800 per patient.

Indirect calorimetry is the recommended method for determining patients' resting energy expenditure (REE). A 2015 estimate showed that only 2% of ICUs were regularly using indirect calorimetry. Predictive equations have therefore been the most commonly practiced method of determining energy needs; however, the literature clearly indicates that each equation has a large potential for error. This makes it difficult to accurately predict an individual patient's energy requirements during critical illness. In general, predictive equations estimate accurately only 50% of the time in ICU patients⁴.

² Thibault R, Pichard C. Nutrition and clinical outcome in intensive care patients. Curr Opin Clin Nutr Metab Care 2010; 13(2):177-83

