5.5. Schedule of Activities (SoA)

Subject: smART Plus Comparative Study Protocol - Beilinson

Procedures	Screening/ enrollment	Medical Device Placement	Ongoing use	Termination
Day	1	1(T)	Up to 14	1 up to 14
Informed Consent	T+C			
Eligibility Criteria	T+C			
Physical Exam	T+C			
Pregnancy test (if applicable)	T+C			
Videotaping		T+C	T+C	
Vital Signs		T+C	T+C	T+C
REE or calorimeter/spirometer measurement		T+C	T as needed and according to procedures	
Lab Data			T+C	T*+C*
Medical Device Administration		T	T	
GRV Measurements			T+C as needed and according to procedures	
Urine monitoring			T as needed and according to procedures	
Adverse Events	T+C	T+C	T+C	T+C
Concomitant Medication		T+C	T+C	T+C
Information regarding nutritional supplement administration		T+C	T+C	

T – group A – "Treated"

C – group B – "Control"

* - For T only – obtained retroactively 24 hours prior the feeding tube insertion and during the ongoing study

6. Preparation/Handling/Storage/Accountability

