2.3 Length of stay:
Sample size rationale:

The rationale for sample size calculation is based on a difference in length of stay between the tested group (with smART+ System) and the current standard practice (group B).

Sample size justification:

The comparison between groups in ventilation days is reflected by Effect size.

A sample size of 100 in each group will have 90% power to detect an **effect size of 0.46** using a two group t-test with a 0.05 two-sided significance level. [1, 2]

References:

9.2 Endpoints analysis:
9.2.1 General:

All measured variables and derived parameters will be listed individually and, if appropriate, tabulated by descriptive statistics.

 ART MEDICAL PATIENT SAFETY TECHNOLOGY	Number: CRO-C-2822	Date issued: 01-Mar-2021
	Rev.06	Page 31 of 35

Subject: smART Plus Comparative Study Protocol - Beilinson

For categorical variables summary tables will be provided giving sample size, absolute and relative frequency and 95% CI (Confidence Interval) for proportions by study arm.

For continuous variables summary tables will be provided giving sample size, arithmetic mean, standard deviation, coefficient of variation (CV%), median, minimum and maximum and 95% CI (Confidence Interval) for means of variables by study arm.

All tests will be two-tailed, and a p value of 5% or less will be considered statistically significant.

The data will be analyzed using the SAS® version 9.4 (SAS Institute, Cary North Carolina).

9.2.2 Primary endpoint:

The two-sample T-test or Non-parametric Wilcoxon-Mann-Whitney Rank sum test for independent samples (as is appropriate) will be applied for testing the statistical significance of the difference in feeding efficiency between the study groups.

9.2.3 Secondary endpoints:

- The two-sample T-test or Non-parametric Wilcoxon-Mann-Whitney Rank sum test for independent samples (as is appropriate) will be applied for testing the statistical significance of the difference in number of ventilation days (Evaluated by the number of hours of etCO2 from the hospital electronic records) between the study groups.

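### The only tested primary variable is net ml over VTBD, so a significant result shows better delivery against VTBD, not the two-sided optimization that Section 2.1 defines

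*Combined protocol and SAP*

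**What the plan says.** Section 2.1 sets a two-sided objective: "Optimization is defined as the ability of the system to provide adequate nutrition (not overfeed or underfeed", in comparison with standard of care. Two parameters are listed for analysis and comparison: the caloric target, and "Volume of patient nutritional intake value versus actual patient need". As a part of that evaluation, Section 2.1 adds "feeding efficiency calculation ((Net nutrition delivered [ml])/ (VTBD [ml])) should be calculated for the days" on which the patient was under an order for enteral feeding. VTBD is explained neither there nor in the abbreviation list. It is presumably the volume to be delivered.

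Section 9.1 bases the sample size on feeding efficiency alone. Its effect size is signed, tested minus control over the common SD: 0.70, with 50 per group, 90% power and two-sided alpha 0.025. Section 9.2.2 gives one primary test, a t-test or Wilcoxon-Mann-Whitney test for "testing the statistical significance of the difference in feeding efficiency between the study groups". No section gives intake versus need a full formula, a tolerance band or a test.

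On the reference value, group A staff program feeding after a smART+ REE measurement (5.2.5, 5.2.6). In group B the target may come from REE, a calorimeter or another method (5.3.2, 5.3.3). The Schedule of Activities plans "REE or calorimeter/spirometer measurement" at device placement in both groups, but during ongoing use only in the treated group.

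**The concern.** The claim has two directions and refers to need. The test has one direction and refers to VTBD. Overfeeding is not a side issue here: Section 1.2.1 says that "overfeeding, even for short periods of time, can lead to hyperglycemia and increases time on the ventilator", and Section 1.8.2 presents reduced overfeeding as a benefit of the device.

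Two mechanisms separate the test from the claim.

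- **Through the order.** If VTBD is the ordered volume, the ratio does not register whether the order matched need. The calculating half of the primary objective is then untested.
- **Through delivery above VTBD.** No cap or band is stated. A patient above 1 raises the group mean and cancels a patient below 1.

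At stake is the headline conclusion. The plan, followed exactly, could announce optimization without having tested whether patients were fed closer to their needs.

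**Working it through.** **1. The plan's own figure.** Inputs from 9.1: d = 0.70, two-sided alpha 0.025, power 90%.

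Normal approximation: n = 2(z₀.₉₈₇₅ + z₀.₉₀)²/d² = 2(2.2414 + 1.2816)²/0.49 = 50.7, so 51 per group. With the noncentral t, n is 52, and power at 50 per group is 88.8%. The stated 50 reproduces within rounding, so the sizing arithmetic is not the problem.

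**2. What the ratio registers.** By identity,

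net/need = (net/VTBD) × (VTBD/need).

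The primary test sees only the first factor. Illustration with an assumed need of 1500 ml and VTBD read as the order:

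| VTBD (ml) | Net (ml) | Efficiency | Net/need |
|---|---|---|---|
| 1500 | 1500 | 1.00 | 1.00 |
| 1800 | 1800 | 1.00 | 1.20 |
| 1200 | 1200 | 1.00 | 0.80 |
| 1500 | 1800 | 1.20 | 1.20 |
| 1800 | 1500 | 0.83 | 1.00 |

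Rows 2 and 3 are missed. Row 4 scores above the ideal. Row 5 meets need exactly and scores worse.

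**3. Signed difference versus distance from target.** Suppose instead that VTBD equals the adequate volume. The documents give no mean or SD, so assume normal data with equal SD σ, and let μ be a group's mean deviation from target. Then

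E|x| = σ√(2/π)·exp(−μ²/2σ²) + μ[1 − 2Φ(−μ/σ)].

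This depends only on the size of μ. With the device mean above the control mean, the device arm is further from target exactly when the midpoint of the two means lies above target.

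The table uses SD units, 50 per group, alpha 0.025 and 20,000 simulated trials per row, with the device always 0.70 SD above control.

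| Control / device mean | Mean absolute deviation, control / device | Effect on absolute deviation | Ratio test favours device | Absolute-deviation test favours device / control |
|---|---|---|---|---|
| −1.00 / −0.30 | 1.167 / 0.834 | 0.46 for device | 89% | 52% / 0% |
| −0.70 / 0 | 0.986 / 0.798 | 0.28 for device | 89% | 20% / 0% |
| −0.35 / +0.35 | 0.846 / 0.846 | 0 | 89% | 1.2% / 1.2% |
| 0 / +0.70 | 0.798 / 0.986 | 0.28 against device | 89% | 0% / 20% |
| +0.35 / +1.05 | 0.846 / 1.201 | 0.49 against device | 89% | 0% / 57% |

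The planned test gives the same answer in every row.

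**4. The same in percentage points, assuming SD 20.** The planned effect is then 0.70 × 20 = 14 points.

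| Control / device mean | Mean absolute deviation from 100%, control / device |
|---|---|
| 70% / 84% | 31.2 / 20.8 |
| 80% / 94% | 23.3 / 16.7 |
| 96% / 110% | 16.3 / 17.9 |

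The crossover is at 93% / 107%. The reversal in the last row is 1.6 points, about 0.13 SD of absolute deviation. Separately, a group split evenly between 70% and 130% averages 100% with every patient 30 points off target.

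**5. Power of an added absolute-deviation test.** Power ≈ Φ(d√(n/2) − 2.2414). At 50 per group, d = 0.283 gives 20% and d = 0.463 gives 53%, close to the simulated 20% and 52%. At the full 100 per group, the same formula gives Φ(2.001 − 2.241) = 40% and Φ(3.274 − 2.241) = 85%.

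**The case against.** Four points on the other side carry weight.

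- **A reader might infer that the ratio rewards overfeeding in general.** It does not. Overfeeding through too high an order leaves the ratio unchanged, so it is missed, not rewarded. The ratio rises only when net delivery exceeds VTBD. No section describes that happening: Section 1.7 speaks of making up lost feeding time and discarded residuals, and the numerator is net of losses. With no cap stated it can happen, but nothing shows that it is likely.
- **A reader might infer that the device could readily win while feeding worse.** Section 1.2.1 points the other way: more than 74% of ICU patients did not receive at least 80% of prescribed nutrition. With both arms under-delivered, ratio and absolute deviation agree in direction. A reversal needs the midpoint of the arm means to lie above target, and the means used here are assumptions.
- **A reader might infer that need is ignored.** Section 2.1 names it. Under 9.2.1, measured and derived variables are tabulated by arm with SD, minimum and maximum, where a 70%/130% split would show. The gap is that intake versus need has no full formula and no test. A descriptive table sets no condition on the claim.
- **Different methods of setting the target are partly the intervention.** That is fair, since automatic calculation is in the objective. It also means that the ratio does not isolate the calculating half.

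A further caution concerns the remedy. A reference based on baseline REE still differs by arm in equipment, may be missing for some controls, and is a single value for up to 14 days. Section 1.2.1 describes starting at half the calorie goal, so absolute deviation from the full target would count planned ramp-up as error. These points must be settled in advance. They do not remove the mismatch.

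**Conclusion.** The mismatch is real under either reading of VTBD. If VTBD is the order, the test does not register whether the order met need. If VTBD reflects need, the test is still signed and uncapped. A significant result supports better delivery against VTBD. It does not by itself support optimization as Section 2.1 defines it.

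The size depends on where the arms lie. With normal data, equal SD and a 0.70 SD difference, the planned test favours the device in about 89% of trials. The effect on absolute deviation runs from 0.46 in its favour to 0.49 against it across the scenarios examined. In the under-delivery scenarios the direction agrees, but the effect shrinks to 0.28 to 0.46. The documents support neither the view that feeding efficiency is unusable as a primary variable nor the view that a misleading reversal is probable.

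**What to change.** - **Section 2.1:** define VTBD, including who sets it, when it may change, and whether it is the ordered volume or derived from measured need.
- **Sections 9.1 and 9.2.2:** keep feeding efficiency as the sized primary. Add a prespecified key supportive analysis of each patient's mean absolute daily deviation, |net delivered/target − 1|, with over- and under-delivery shown separately. Repeat it in kcal against the measured REE or calorimeter target, counting any parenteral calories recorded under 5.2.8 and 5.3.5.
- **State in advance how the analysis handles** control patients without a measured REE, early ramp-up days, later REE changes (re-measurement is scheduled in the treated group only), and the different measuring equipment in each arm.
- **Claim:** use the term optimization only if this analysis supports it. Otherwise restrict the conclusion to delivery of the volume to be delivered.

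The cost is mainly SAP and endpoint wording, since the inputs are already planned for collection. The downside is that the 0.70 effect size does not carry over to the added variable. In the assumed under-delivery scenarios its power is about 20% to 52% at 50 per group, and roughly 40% to 85% at 100 per group. A non-significant supportive result should therefore be reported with its confidence interval and not read as evidence of no difference.
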